20.2 SUBJECT WITHDRAWAL

All subjects are free to withdraw from participating in this study at any time and for whatever reason, specified or unspecified, without prejudice.

Reasons for withdrawal (subjects refuse to return for any remaining study visits) or discontinuation (subjects who prematurely stop the active treatment) at any time during the study may include but are not limited to the following:

- Safety reasons, either at the discretion of the Investigator or at the subject's request. In particular, subjects will be discontinued from the study if they develop severe complications of celiac disease that require intensive treatment (EATL, perforation, etc.).
- Protocol violations at the discretion of the Sponsor.
- Subject noncompliance to study procedures or schedule
- Concomitant therapy that could interfere with the results of the study (the Investigator will report all such information on the eCRFs and decide, in accordance with the Sponsor, whether the subject is to be withdrawn).
- Subject's decision to withdraw at any time.

Subjects who withdraw prior to receiving the study drug are considered screen failures.

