22.7 EXPLORATORY ENDPOINTS

Exploratory endpoints will be described in the SAP and will include:

- Reduction in aberrant and abnormal IELs by flow cytometry, immunohistochemistry and TcR clonality analyses (including % patients with normalization in IELs)
- PGA and PtGA
- Quality of Life Assessments:
 - SF-12 v. 2
 - EQ-5D
- Biomarkers of disease activity
- PK, PD, and PK/PD correlations
- CeD PRO

The exploratory variables will be tabulated by treatment group and time point (if feasible) using the ITT or PP populations as appropriate.

The exploratory variable CeD PRO will be analyzed using the same method as for the GSRS and CeD-GSRS.

Pharmacokinetics of AMG 714 in RCD-II patients will also be characterized using nonlinear mixed-effects modeling, including evaluation of effects of major covariates (e.g., weight or BMI, BSA, sex, biochemical parameters and disease characteristics at baseline) on AMG 714 exposure.

For PK/PD correlations, individual patients' exposure measures obtained from the PK analysis will be graphically assessed with select PD endpoints and if associations are observed will be further elucidated with modeling and/or summaries by quartiles of exposure.

Exploratory exposure-response analysis will be performed for efficacy, safety, and biomarker measures. These exploratory analyses will be assessed with appropriate descriptive statistics and graphical displays.

Change from baseline (by time point) will also be presented for reduction in aberrant IELs by immunochemistry and TcR clonality analyses, PGA and quality of life assessments (SF-12 v. 2 and EQ-5D).

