8.1 Data sets to be analysed

The populations for analysis will be the intention to treat (ITT, safety population, at least one dose of the investigational product received) and the per protocol population (PP, efficacy, i.e., available and evaluable pre- and post-biopsy information [Week 6]).

PP population: the PP population will exclude non-evaluable subjects and subjects with major protocol deviations thought to impact the ability to assess the effect of treatment. The PP population will also exclude atypical RCD-II patients (patients with a different phenotype of the aberrant IELs) for the purpose of analysis of Immunological Response 1 and 2; however, they will be included in all other efficacy assessment where a sensitivity analysis maybe performed excluding these subjects if these subjects are determined to be influential. Exclusion of subjects from the PP set will be reviewed, documented and approved before the study is unblinded to the study Sponsor.

Non-evaluable subjects will include subjects missing one of the two biopsies (or with biopsies of insufficient quality to generate valid data as determined by the Sponsor prior to database lock) and subjects dropping out of the study before Week 6. If a discontinuation occurs on or after Week 6 and the second biopsy is collected, then the subject is considered evaluable.

Atypical patients may also be analysed as a separate population if the results and sample size suggest such analysis is valuable.

The following major protocol deviations, as determined by the Sponsor prior to database lock, will lead to exclusion of subject from the PP population and will be thoroughly documented in the clinical study report:

- Intake of any forbidden concomitant medication or participation in other medical procedures, in case there is reason to believe, by the judgement of the Sponsor or investigator, that such concomitant medication/procedures would have a significant effect on the efficacy data obtained;
- Significant deviations from the inclusion/exclusion criteria of the study not previously approved by the Sponsor and determined prior to database lock to have impact on interpretation of results.

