8.2.3 Handling of data from discontinued subjects

Subjects who are randomized but discontinue before receiving study treatment will not be included in any efficacy or safety analysis, but will be included in the disposition of subjects table. Subjects who receive at least one dose of study treatment will be included in ITT analysis population.

Subjects discontinuing from study drug administration before Week 6 will be excluded from the PP analysis population and the second biopsy will not be collected. Subjects discontinuing on or after Week 6 will be included in the PP analysis population sets if the second biopsy can be collected (in case a subject is lost to follow-up on or after Week 6 and a biopsy cannot be collected, the subject is considered non-evaluable and excluded from the PP population).

Subjects will be considered study completers at Visit 8 (Week 12/Day 84), regardless of whether or not the Final Study Visit (Visit 9; Week 16/Day 112) is attended.

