8.7 Exploratory analysis

The exploratory endpoints of the study are:

- Reduction in aberrant and abnormal IELs by flow cytometry, immunohistochemistry and TcR clonality analyses (including % of patients with normalization in IELs);
- PGA and PtGA;
- Quality of Life Assessments:
 - SF-12 v. 2;
 - EQ-5D;
- Biomarkers of disease activity;
- PK, and PK/PD correlations;
- CeD PRO;
- Assessment of the gluten-free diet (iVYLISA GIP stool test and dietician consultation).

8.7.1 Reduction in aberrant and abnormal IELs by flow cytometry, immunohistochemistry and T cell receptor (TcR) clonality analyses

Aberrant IELs were narrowly defined in [Section 2](#) for the purpose of primary and secondary endpoint analysis. In addition to these aberrant IELs, found by definition in the intestinal epithelium, cells with identical characteristics can be measured in the *lamina propria* of the mucosa (“aberrant IELs in the *lamina propria*”) and -should the aberrant IELs leave the gut mucosa to spread to other tissues- in peripheral blood also (“aberrant IELs in blood”). These cells will be assessed.

In addition to the frequency of aberrant IELs, multiple markers will be studied in IELs which may identify other abnormal IELs, defined as IELs with an inflammatory (e.g., Granzyme B-positive) or otherwise abnormal phenotype or a phenotypically normal population with abnormal prevalence in blood or biopsy tissue. These phenotypes and abnormalities may also be assessed in aberrant IELs.

IEL abnormalities may be detected by several methods, such as flow cytometry, immunohistochemistry, or with TcR clonality analyses (a method to detect abnormal and also aberrant IELs by quantifying the characteristic T cell Receptor, which is monoclonal in aberrant IELs).

While aberrant IELs are pre-defined in primary and secondary endpoints based on surface and intracellular CD3 expression by flow cytometry (and CD8 expression by IHC), at this time it is not possible to predict which other populations of IELs may be abnormal and may require analysis, which will be done ad-hoc in an exploratory fashion.

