Percentages and counts of aberrant and abnormal IELs by flow cytometry, immunochemistry or TcR clonality, and changes from baseline will be presented using summary statistics by treatment group and visit. Specifically, the % of Granzyme B-positive aIELs and IELs, as well as the mean fluorescence intensity of the Granzyme B expression in those and other cell types, will be summarized and analysed by treatment group.

PP population will be used for summarizing these results.

These analyses will be done internally at Celimmune.

8.7.2 Physician Global Assessment of Disease (PGA) and Patient Global Assessment of Disease (PtGA)

The PGA is designed to be used by the Investigator or qualified designee to assess the subjects' disease activity at the time points specified in the study schedule of events (Appendix 1). An attempt should be made to use the same assessor at each specified time point. Part B of the PGA is designed to assess physician perception of change in disease activity. Part B should be completed as per the schedule of events (Appendix 1) beginning after Visit 1, Week 0/Day 0.

The PtGA is designed to be used by the subject to assess perception of disease activity at the time points listed in Appendix 1. Part B of the PtGA, is designed to assess subject perception of change in disease activity and should be completed as per the schedule of events (Appendix 1) beginning after Visit 1, Week 0/Day 0.

Both PGA and PtGA are filled in on paper.

PGA and PtGA will be tabulated by treatment group, visit and part (PGA/PtGA part A, PGA/PtGA part B). Change from baseline in PGA and PtGA part A will be presented by treatment group and visit. All PGA and PtGA results will also be listed. Mean PGA and PtGA results will also be plotted by visit and treatment group.

As an exploratory assessment, Week 12 PGA scores will be dichotomized for an outcome endpoint where scores ≤ 2 will be considered treatment success and scores > 2 will be considered treatment failure. Assessment of differences in treatment proportions will be conducted.

ITT population will be used for summarizing PGA and PtGA results.

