8.7.4 Biomarkers of disease activity

Several biomarkers of disease activity may be analysed in serum and in biopsy tissue at the time points specified in [Appendix 1](#), if available and deemed appropriate by the Sponsor. The biomarkers of interest include:

- Serum IL-15 (pg/mL);
- Serum Granzyme B (pg/mL);
- Serum CRP (mg/L);
- Serum albumin (g/dL);
- Flow NKG2D (% of positive cells; mean fluorescence intensity, MFI);
- Flow GzmB (% of positive cells; MFI);
- Flow CD122 (% of positive cells; MFI).

In addition, other exploratory biomarkers may be analysed, if deemed appropriate.

The biomarkers of disease activity will be described by summary statistics, along with the change from baseline values and tabulated by treatment group and visit, if applicable. All individual results will be listed by visit. Mean curves of biomarkers of disease activity will also be plotted by visit and treatment group, if applicable. Individual curves of relevant biomarkers may also be created, if deemed appropriate.

Flow cytometry biomarkers will be analysed internally by Celimmune.

ITT and PP analysis populations will be used for summarizing biomarker results depending on the type of marker (biopsy-derived, PP; continuous variable, ITT).

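### SAP 8.7.1 puts aberrant cells in peripheral blood in the per-protocol set, against the SAP's own Table 1 rule that variables not needing a biopsy use ITT

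*SAP*

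**What the plan says.** SAP 8.7.1 extends the aberrant-cell analysis beyond the epithelium. Cells with the same characteristics are to be looked for in the lamina propria and, "should the aberrant IELs leave the gut mucosa to spread to other tissues- in peripheral blood also". The planned output, split by arm and visit, covers every compartment and method together: "Percentages and counts of aberrant and abnormal IELs by flow cytometry, immunochemistry or TcR clonality, and changes from baseline will be presented using summary statistics". The section's only statement on the analysis set is "PP population will be used for summarizing these results", with no exception for blood.

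Three other places give a different or looser rule:

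- SAP 8.1, Table 1, footnote 1, which covers the secondary and exploratory/PD variables, keeps PP for variables that depend on a biopsy and gives ITT to the rest.
- SAP 8.7.4, on biomarkers, chooses the set "depending on the type of marker (biopsy-derived, PP; continuous variable, ITT").
- Protocol 22.7 leaves the choice open: "The exploratory variables will be tabulated by treatment group and time point (if feasible) using the ITT or PP populations as appropriate".

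Membership of PP is set in SAP 8.1 and 8.2.3. "Non-evaluable subjects will include subjects missing one of the two biopsies", those whose biopsies are of insufficient quality, and those who drop out before Week 6. SAP 8.2.3 adds: "Subjects discontinuing from study drug administration before Week 6 will be excluded from the PP analysis population". Subjects who discontinue on or after Week 6 are kept if a second biopsy is collected and can be evaluated.

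**The concern.** PP is a reasonable set for a measure that exists only when two biopsies exist. Blood flow cytometry is not such a measure. Protocol Table 1 schedules whole blood for it at Visits 1, 4, 6, 8 and 9, independently of endoscopy. Applying PP to it discards samples that were taken, for a reason unrelated to whether the blood result is valid.

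The reason may be related to prognosis. Protocol 20.2 says "subjects will be discontinued from the study if they develop severe complications of celiac disease that require intensive treatment (EATL, perforation, etc"), and Protocol 11.4 lets the investigator forgo the exit endoscopy because of the subject's condition. Being outside PP can therefore depend on how the subject is doing. The SAP presents circulating aberrant cells as what would be seen if these cells spread beyond the gut mucosa, so this is a poor measure on which to lose such subjects by rule.

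There is also a reproducibility problem. Two competent analysts, one following the sentence in 8.7.1 and the other the footnote in Table 1, would produce different tables from the same data.

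**Working it through.** No figure in the plan rests on this point, so the check is a comparison of rules followed by simple arithmetic on the planned arm sizes.

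**1. Which rule governs blood?** Blood flow cytometry does not depend on a biopsy. Under Table 1 footnote 1 it belongs to ITT; under the closing sentence on populations in 8.7.1 it belongs to PP. SAP 8.7.4 points the same way as Table 1, but it describes markers in serum and biopsy tissue, so it is a parallel and not the governing text. The SAP states no order of precedence. The conflict is unresolved.

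**2. Who is affected?** Sources: PP rules in SAP 8.1 and 8.2.3, blood schedule in Protocol Table 1, follow-up after stopping drug in Protocol 20.2.1. All rows assume at least one dose and no major deviation.

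| Subject | Blood that could exist | 8.7.1 (PP) | Table 1 (ITT) |
|---|---|---|---|
| Stops drug before Week 6, continues visits | Weeks 0, 4, 8, 12, 16 | Out | In |
| Leaves study after Week 4, before Week 6 | Weeks 0 and 4, perhaps early termination | Out | In |
| Leaves study before Week 4 | Week 0, perhaps early termination | Out | In, for the samples taken |
| Leaves on or after Week 6, no usable second biopsy | Weeks 0 and 4, perhaps later | Out | In |
| Completes, second biopsy unusable | Weeks 0, 4, 8, 12, 16 | Out | In |
| Leaves on or after Week 6, usable second biopsy | Weeks 0 and 4, perhaps later | In | In |

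The first row is by design: Protocol 20.2.1 asks for continued evaluation where possible but states that the second biopsy is not collected. Subjects removed from PP for major deviations are also lost to the blood summary under 8.7.1.

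**3. How large is one exclusion?** With the planned 16 and 8 subjects:

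- AMG 714: 1/16 = 6.25%
- Placebo: 1/8 = 12.5%

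**4. How likely is at least one?** The documents give no dropout rate, and the sample size calculation in Protocol 22.1 allows for none. As an assumption, let each of 24 subjects independently fall outside PP with probability r. The expected number is 24r and the chance of at least one is 1 − (1 − r)^24.

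| r (assumed) | Expected number outside PP | Chance of at least one |
|---|---|---|
| 5% | 24 × 0.05 = 1.2 | 1 − 0.95^24 = 71% |
| 10% | 24 × 0.10 = 2.4 | 1 − 0.90^24 = 92% |
| 20% | 24 × 0.20 = 4.8 | 1 − 0.80^24 = 99.5% |

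So the two rules probably give different tables even at a low rate. This says nothing about the direction of the difference.

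**The case against.** The strongest reply is that the SAP already contains the right rule. Table 1 footnote 1 can be read as governing all exploratory variables, with the sentence in 8.7.1 written with biopsy tissue in mind. On that reading the text is loose and nothing is lost. This stands to the extent that the defect is an inconsistency, not a settled decision to analyse blood in PP only. It does not remove the need for a correction, because 8.7.1 is the specific section and it explicitly includes blood.

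The stakes are also low. The endpoint is exploratory, part of it is declared ad hoc, and the go/no-go reading in Protocol 13.1 rests on the two Immunological Responses. This stands.

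Nor would moving to ITT cure informative loss. Carrying values forward is confined to biopsy variables (SAP 8.2.2), so a subject who leaves the study contributes no later blood values under either set. This stands too: the change recovers the samples that were taken and no more.

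A reader might go further and infer that everyone who leaves early disappears, that the exclusion makes both arms look better, or that an EATL case would be hidden. The documents do not support these readings. Later leavers with a usable second biopsy stay in PP. PP also drops subjects for poor biopsies, prohibited medication and eligibility deviations, none of which need track progression. Protocol 1.2.2 treats high-grade EATL and dissemination of the low-grade proliferation as separate outcomes, so withdrawal for EATL cannot be equated with aberrant cells in blood. A clinical case would still appear among adverse events with narratives (SAP 8.8.1), in the reasons for discontinuation (SAP 8.3) and in the imaging listing for ITT (SAP 8.8.6.3). None of these outputs replaces the by-arm blood summary, and 8.7.1 does not itself promise a listing.

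**Conclusion.** The point holds as a contradiction within the SAP with a limited consequence. As written, 8.7.1 leaves treated subjects out of the peripheral-blood summary if they stop before Week 6 or lack a usable second biopsy, although Table 1 footnote 1 would include them. Each such subject is 6.3% of the AMG 714 arm or 12.5% of the placebo arm at the planned sizes.

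The exclusion may be informative, given the discontinuation rule for severe complications and the discretion over the exit biopsy. That is a possibility and not a demonstrated bias. Its direction and size cannot be obtained from the documents, and the exclusion rates used above are assumptions. A reader might picture a table of subjects with newly detected circulating cells that differs between the two sets, but 8.7.1 plans only summary statistics of percentages, counts and changes, so no such proportion is a planned output.

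Because the endpoint is exploratory and progression remains visible elsewhere, this is a minor-priority correction.

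**What to change.** In SAP 8.7.1, replace the single population sentence with a split. PP applies to the epithelial, lamina propria, immunohistochemistry and biopsy TcR measures. Peripheral-blood flow cytometry is summarised in the ITT set, by treatment group and visit, using all available samples, in line with Table 1 footnote 1. It would help to state the number of subjects contributing at each visit and to add an ITT listing of the blood results, since 8.7.1 promises none.

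The cost is one sentence, one population flag and, if wanted, one listing. No new data are needed.

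The sampling text should be reconciled at the same time. Protocol Table 1 and Appendix B include whole-blood flow cytometry at early termination, while the visit list in Protocol 11.4 omits it. Without that sample, a subject who leaves before Week 4 has only a baseline value, and the ITT summary gains little from that subject.

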APPENDIX E. SAMPLE PHYSICIAN GLOBAL ASSESSMENT OF DISEASE/RATING OF CHANGE

Part A: To be completed by the physician at all required visits.

Based on the information available, chose the box that best represents the subject's current overall disease activity:

Inactive Disease Mild Disease Moderate Disease Severe Disease

Symptoms & Signs

Category	Abdominal Pain	Diarrhea	Fatigue	Activity	Lab Tests
Inactive Disease – Minimal or no symptoms thought to be related to RCD-II	Asymptomatic	One or two episodes that resolve spontaneously	Asymptomatic or symptoms felt to be due to another disorder (i.e., depression)	Asymptomatic or symptoms felt to be due to another disorder	Normal or minimal abnormalities
Mild Disease – Mild recurring or persistent symptoms thought to be secondary to RCD-II	Mild pain secondary to RCD-II occurring several times a week	Mild diarrhea thought to be secondary to RCD-II	Asymptomatic or mild symptoms that resolved spontaneously	Asymptomatic or symptoms felt to be due to another disorder	Persistent and significant laboratory abnormalities felt to be secondary to RCD-II with no or mild associated symptoms
Moderate Disease – Moderate or a combination of mild and moderate recurring or persistent symptoms thought to be due to RCD-II	Moderate abdominal pain thought to be secondary to RCD-II	Moderate diarrhea thought to be secondary to RCD-II	Significant fatigue thought to be due to RCD-II	In ability to maintain normal activities due to fatigue or other symptoms	Significant laboratory abnormalities felt to be secondary to RCD-II with mild or moderate associated symptoms
Severe Disease – Severe or a combination of moderate and severe recurring or persistent symptoms thought to be related to RCD-II	Severe abdominal pain thought to be secondary to RCD-II	Significant diarrhea thought to be secondary to RCD-II	Significant fatigue thought to be secondary to RCD-II	Severe impairment of normal activities due to fatigue or other symptoms	Significant laboratory abnormalities felt to be secondary to with moderate to severe associated symptoms

Part B: To be completed by the physician at all required visits after Visit 1; Week 0/Day 0.

Please choose one of the following options that best describes the patient's overall change in their celiac symptoms since their baseline study visit:

- VERY MUCH BETTER
- MODERATELY BETTER
- A LITTLE BETTER
- NO CHANGE
- A LITTLE WORSE
- MODERATELY WORSE
- VERY MUCH WORSE

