- To assess the pharmacokinetics (PK), pharmacodynamics (PD), and PK/PD associations of AMG 714.

The **exploratory endpoints** of the study are:

- PK;
- PD;
- Exposure/response (PK/PD).

PK data will be tabulated by timepoint. Exploratory PD endpoints are aberrant and abnormal IELs by flow cytometry, immunochemistry and T cell receptor (TcR) clonality analyses, Physician Global Assessment of Disease (PGA) and Patient Global Assessment of Disease (PtGA), Quality of Life Assessments (i.e. SF-12 v. 2 and EQ-5D), biomarkers of disease activity (i.e., serum IL-15, CD122 and granzyme B) and Celiac Disease Patient Reported Outcome (CeD PRO). The exploratory PD endpoints will be evaluated by investigating the change from baseline and weekly scores, if applicable, of AMG 714 dose arm and placebo arm.

3 Study type and design

CELIM-RCD-002 is designed to be a Phase 2a randomized, double-blind, placebo-controlled, parallel-group study to evaluate the efficacy and safety of AMG 714 for the treatment of adult patients with RCD-II, an in situ small bowel T cell lymphoma.

After signing informed consent, subjects will be screened for the study. All subjects who meet the study entry criteria will be randomized at a 2:1 ratio to receive either 8 mg/kg AMG 714 or placebo for a total of 7 times over 10 weeks, with evaluation of the primary endpoint at Visit 8 (Week 12/Day 84).

AMG 714 (N=16) or placebo (N=8) will be administered at the clinical site in a double-blind fashion via intravenous (IV) infusion of approximately 120 minutes (2 hours) duration.

Subjects will remain confined to the study site for a minimum of 1 hour after the administration of study medication. During this time the investigator and study site staff will assess the subject for adverse events (AEs). As per [Appendix 1](#), PK samples are to be collected prior to the infusion and 1 hour after the infusion, at the end of this observation period. The beginning and end of each infusion, as well as the PK sample collection times, will be recorded.

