where $\mu_{AMG\ 714}$ and $\mu_{placebo}$ denote the mean baseline to Week 12 relative (%) change in % aberrant IELs vs total IELs as assessed by flow-cytometry in the AMG 714 and placebo arm, respectively. The hypotheses will be tested using a two-sided, 0.10 level of significance.

7 Estimation of sample size

The CELIM-RCD-002 study is an exploratory proof-of-concept (POC) study of an experimental medication, AMG 714, in RCD-II patients. While it will be the first such study sponsored by a pharmaceutical company, the straightforward design is based on several academic studies (Goerres *et al*, 2003; Brar *et al*, 2007; Tack *et al*, 2011a, 2011b) as well as on the nonclinical proof-of-principle signal obtained with AMG 714 in intestinal explants from patients with RCD-II (Malamut *et al*, 2010).

The sample size is based on the size of previous academic studies. Published prospective academic studies have ranged from 13 to 18 subjects total (Tack *et al*, 2011a, 2011b) and CELIM-RCD-002 will be the largest prospective trial ever conducted in RCD-II, a very rare malignant disease.

The sample size of 24 subjects (16 subjects in AMG 714 arm and 8 subjects in placebo arm) has been calculated to achieve at least ~ 80% power to detect a 20 percentage point difference in the primary endpoint, the difference in the baseline-to-Week 12 reduction of % aberrant IELs vs total IELs between the AMG 714 arm and placebo arm.

This sample size calculation was based on the following assumptions:

- Two-sided type one error rate $\alpha = 0.1$.
- Power $1-\beta = 0.8$.
- Analysis method: one-way analysis of variance (ANOVA) by SAS[®] (proc power).
- 2:1 allocation ratio between the AMG 714 and placebo arms.
- Common SD = 17.4 for the baseline to Week 12 reduction in % aberrant IELs as assessed by flow-cytometry.

- Mean change of 20 percentage points and 0 percentage points in the baseline to Week 12 reduction in % aberrant IELs in the AMG 714 and placebo arms, respectively.

The standard deviation used for the sample size calculation is computed from the % aberrant IELs (obtained by flow-cytometry) data from 13 subjects treated with cladribine (subset of the subjects reported in Tack et al, 2011).

8 Statistical methods

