8.2 General statistical considerations

Descriptive statistics (e.g. mean, median, standard deviation (SD), minimum (MIN), maximum (MAX), and number of subjects with an observation (N) or missing observation (NMISS)) are used for summarizing continuous variables. Additional statistics will be provided for PK-related data, including the geometric mean, SD of log-transformed data, geometric CV% and geometric N (i.e. number of subjects with an observation that are included in the natural logarithmic transformation).

Frequencies and percentages are used for summarizing categorical variables.

All summary statistics will be presented by treatment arm and if repeated measures, then by visit/collection time point.

All listings will be created using ITT population. The PP and ITT flags for each subject will be included in all listings.

All tests will be two-sided, if not stated differently. P-values smaller than 0.1 (for primary hypothesis) or 0.05 (all other hypotheses) will be considered statistically significant. In addition to the inferential statistics, 90% or 95% confidence intervals will be constructed. For the primary endpoint a 90% confidence interval of the treatment difference will be

constructed. Ninety-five percent (95%) confidence intervals will be constructed for the individual treatment point estimates.

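### The only between-arm PGA comparison splits Week 12 scores at 2, leaves out baseline, and does not say which part of the form or what coding it uses

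*SAP*

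**What the plan says.** SAP 8.7.2 covers both parts of the Physician Global Assessment. It tabulates Parts A and B by arm and visit, presents Part A change from baseline by arm and visit, lists all results and plots means. One sentence then adds an exploratory outcome: "Week 12 PGA scores will be dichotomized for an outcome endpoint". A score of 2 or less is labelled a success and anything higher a failure. The comparison is given only as "Assessment of differences in treatment proportions will be conducted". No test, covariate or reason for the cut is stated. The SAP document history shows that the split was added in version 2.0. Protocol 22.7 only tabulates the PGA.

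Protocol Appendix E shows the form. Part A has four ordered boxes, "Inactive Disease Mild Disease Moderate Disease Severe Disease". Part B is a seven-option rating of change since baseline, running from very much better to very much worse. The sample form prints no numeric codes. Part A is recorded at Visit 1 and at Week 12 (Protocol Table 1).

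On significance, SAP 8.2 says "P-values smaller than 0.1 (for primary hypothesis) or 0.05 (all other hypotheses) will be considered statistically significant", so 0.05 applies to the PGA.

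**The concern.** There are two problems.

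**The rule cannot be programmed as written.** A cut at 2 means different things under different readings:

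| Reading | Success at 2 or less |
|---|---|
| Part A coded 1–4 | inactive or mild |
| Part A coded 0–3 | inactive, mild or moderate |
| Part B coded 1–7 in printed order | very much or moderately better |

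**Under Part A coded 1–4, success measures status and not change.** Inclusion criterion 4 (Protocol 9.1) does not require current symptoms of patients who were previously treated or are on steroids, and the Part A levels are defined largely by symptoms. Patients can therefore enter already inactive or mild. One who stays mild counts as a success, while one who moves from severe to moderate counts as a failure. Merging four levels into two and leaving out baseline also discards information that an arm of 8 can ill afford to lose. Elsewhere the SAP uses baseline: the primary, Immunological Response 2, VH:CD, total IEL, GSRS, CeD-GSRS and CeD PRO models all include it, and the Marsh endpoint is improvement from baseline.

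At stake is the reading of one exploratory clinical endpoint that carries the label of treatment success.

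**Working it through.** **The plan's own figure.** The SAP says that the sample size "has been calculated to achieve at least ~ 80% power to detect a 20 percentage point difference in the primary endpoint". Inputs are a difference of 20, SD 17.4, two-sided alpha 0.10, and 16 versus 8. The standardised effect is 20/17.4 = 1.149. The noncentrality is 1.149/√(1/16 + 1/8) = 1.149/0.433 = 2.65 on 22 degrees of freedom, which gives power of 82.3%. The next smaller 2:1 design, 14:7, gives 77.3%. The planned size is reproduced, but it concerns the primary endpoint. No power or effect is stated for the PGA.

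**What the split can show at 16 versus 8.** This step needs no assumed effect. With Fisher's exact test at 0.05:

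- Against 2/8 placebo successes, the active arm needs 12/16.
- Against 3/8, it needs 14/16.
- Against 6/8, even 16/16 fails: p = C(8,2)/C(24,2) = 28/276 = 0.10. From 6/8 upward, no result in favour of the active arm can be significant.

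The unnamed test matters. For 16/16 versus 6/8, the uncorrected chi-square is 24 × (16×2 − 0×6)² / (16×8×22×2) = 24,576/5,632 = 4.36, which exceeds 3.84 and is significant.

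**Power under stated assumptions.** None of the PGA inputs below is in the documents.

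- Part A coded 1–4, generated from a latent bivariate normal for baseline and Week 12.
- Latent shift of 0.8 or 1.15 SD; the 1.15 is borrowed from the primary endpoint.
- Baseline to Week 12 correlation 0.3 to 0.7.
- Inactive/mild/moderate/severe proportions of 25/25/25/25, 10/30/40/20, 20/40/30/10 or 5/20/50/25.
- 16 versus 8, two-sided 0.05. The comparator is ANCOVA of the four-level score on treatment and baseline score.

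| Assumed shift | Split, Fisher | Split, chi-square | Four-level ANCOVA |
|---|---|---|---|
| 0.8 SD | 20–23% | 31–36% | 38–55% |
| 1.15 SD | 37–45% | 49–59% | 66–85% |

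Compared setting by setting, ANCOVA gains about 6 to 32 points over chi-square and 17 to 44 over Fisher. Under no effect, ANCOVA rejects about 4.4–5.6% of the time and the uncorrected chi-square 5.3–6.5%, so the gain does not come from an inflated error rate.

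**Wider grid.** Let the shift run from 0.5 to 1.5 SD and add a distribution with 75% of placebo patients inactive or mild. The gap is then about 1 to 38 points against chi-square and 9 to 63 against Fisher. The smallest gaps come with a small shift and low correlation. The largest come with a large shift, high correlation and a mostly mild population. Dropping to two levels accounts for about 1 to 30 points (chi-square) or 8 to 55 (Fisher) before any baseline adjustment.

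**Unchanged mild patients.** In these simulations, patients mild at both visits make up about 13 to 36% of placebo successes.

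**Other coding.** With Part A coded 0–3, the cut at 2 has only about 3 to 22% power (Fisher) at a shift of 1.15 SD.

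**The case against.** The strongest objection is that Part A is not stated. SAP 8.7.2 names Part A for change from baseline but not for the split. Under Part B coded 1–7, a cut at 2 fits the label of success well, baseline is built into the question, and the point about unchanged mild patients disappears. This stands, and it is why the point is conditional. Part A remains the more natural reading because it is the disease-activity rating, while the documents call Part B a rating of change. The ambiguity itself needs correcting on either reading.

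A reader might infer a fixed power loss, or that the trial is underpowered for a PGA effect it was planned to detect. The documents support neither. No PGA effect was planned, and 1.15 is the standardised difference for a flow-cytometry reduction, applied here to a latent PGA scale. Nor is a hypothesis test required by the text: a difference in proportions with a confidence interval would satisfy it.

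A reader might also infer that baseline is ignored altogether, or that the comparison is biased. Part A change is shown descriptively, so a severe-to-moderate improvement would be visible there. Randomisation gives both arms the same expected entry mix, so unchanged mild patients dilute the contrast and do not bias it. With 24 unstratified patients, though, a chance imbalance at entry would go uncorrected.

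Finally, the PGA is exploratory, and the go/no-go rule in Protocol 13.1 rests on Immunological Responses 1 and 2. That stands and limits the importance of the point.

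**Conclusion.** The point holds in conditional form. It is certain from the text that the split is the only between-arm PGA comparison, that it has no baseline term, and that the part and coding are unspecified. If Part A coded 1–4 is meant, unchanged mild patients count as successes and severe-to-moderate improvement counts as failure.

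The direction of the power loss is firm: the full-scale, baseline-adjusted analysis did better in every non-zero setting examined. Its size is not. Roughly 6 to 32 points (chi-square) or 17 to 44 (Fisher) applies to shifts of 0.8 to 1.15 SD under the assumptions listed, within a wider range of about 1 to 63. A single figure would claim more than the documents allow. Because the endpoint is exploratory and does not enter the go/no-go decision, this is an improvement to consider and no threat to the trial's main conclusion.

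**What to change.** In SAP 8.7.2:

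1. Make the between-arm comparison Week 12 PGA Part A on all four levels, with treatment as factor and baseline Part A as covariate, by ANCOVA on the score or rank ANCOVA.
2. Keep the split as a descriptive table. Define it by part and category name instead of by number, and show it overall and by baseline category.
3. State the numeric coding of Parts A and B. If the split was meant for Part B, say so.

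The cost is SAP wording and one more exploratory model; no new data are needed. ANCOVA on the score treats the four levels as equally spaced, which rank ANCOVA avoids. The table by baseline category will have small cells, especially on placebo, and should not be tested.
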